#### **COVID pathology**

- Date of COVID,
- Severity of initial COVID: oxygen requirement, parenchymal extension on CT-scan, non-respiratory symptoms,
- Post-COVID symptoms: dyspnea, fatigue, cough, muscle and/or joint pain, anxiety, agueusia, anosmia, headache, neurological symptoms, gastrointestinal symptoms, palpitations, dizziness.

#### **Additional data available**

- Cardiovascular assessment: HR, cardiac ultrasound, MRI,
- Anxiety/depression questionnaire scores and Chalmers fatigue questionnaire,
- Resting respiratory function: FEV1, FVC, SVC, CI, TLco.
- Helium VA
- 

#### **Symptoms during CPET**

The Borg scale should be used (see [Appendix 3](#)) for the collection of symptoms during CPET. This scale is used to assess the intensity of breathlessness and muscle fatigue during exercise in patients.

### 7.2.2. Physiological Data

In order to get rid of some of the variability of the results, the export of physiological data will only concern the measured data. Additional physiological data will then be obtained by applying the appropriate physiological calculation formulas in a strictly identical way whatever the brand of the ergospirometer is. All these data (measured and calculated) will constitute a file called **Finalized File**.

This Standardized file will constitute the physiological source data used to reach the research objectives of the study.

The content of the Standardized file is imported into a database, which contains only the patient's data.

Eventually, the anonymized clinical and exercise physiological (CPET) data will be transferred to a spreadsheet for statistical analysis. In no case will the statisticians have access to the patient's personal information.

## 7.3. Data transmission and migration

A new CPET Open Source Data platform (CPET-STUDIES.COM), designed by HYLAB with the help of the software development company ASCANIO, is intended to collect clinical and physiological data.

The CPET-STUDIES.COM application transforms the files' original data into a Finalized File.

**Access to the platform will be secured** by identification with a login and a password

- The patient's physiological and clinical data will be encrypted and pseudonymized when migrated and/or entered on the CPET-STUDIES.COM platform,
- The content of the Finalized File will then be imported into a database, which contains only the clinical data associated with the patient's pseudonym.

Clinical data:

Pseudonymized data will be stored separately from the rest of the study and will be encrypted. Moreover, for security reasons, data extraction tools will not decrypt these pseudonymized data.

Physiological data :

Physiological data in the export file will be migrated to a Finalized File which will, in a homogeneous manner, perform:

- cycle-by-cycle averaging of measured variables over the last 20 and 30 seconds of each minute;
- the calculations required to obtain new variables of interest (called *calculated variables*).

This Finalized File will constitute the SOURCE data for this study, exploitable for the research objectives of the study.

Finally, the anonymized data (clinical and EFX) will be transferred to the R statistical software. Under no circumstances will the statistician have access to the personal information of the patient.

#### *7.4. Dissemination or publication of the study results*

It is not in the public interest that the results of a study are never made available or considered, especially by public decision-makers or authorized representatives of the community where the study was conducted. Withholding information or refusing to disclose results can only be justified in exceptional circumstances; for example, when methodological problems encountered during the study render the results meaningless. When it is not possible to present or publish all the results or conclusions of an epidemiological study for reasons of limited space or insufficient time to allow such presentation or publication, the person in charge of the study must guarantee that all persons who might be interested in all the results or conclusions will have access to them upon request.

The main results must be communicated to those who participated in the study or their representatives, as well as to other members of the community where the study was carried out. In this respect, the scientific committee undertakes to transmit the results of the study to all the investigating physicians who participated in it.

#### **Intermediate results**

Intermediate results should always be explicitly stated as such. Intermediate results, as well as raw or previously processed data or any data, results, analyses or conclusions that may be derived from these intermediate results, may not be transmitted to third parties or used in other studies unless such transmission or use is explicitly provided for in the protocol and is specifically approved by the study's manager.

In the event that the study is discontinued for any reason, the presentation or publication of any preliminary or partial results or findings from the study may occur subject to compliance with prior validation procedures. Data or results from the discontinued study should be identified as such in subsequent publications and presentations.

#### **Obligation to publish**

All results of a study, whether the funders are public or private, are the scientific responsibility of the physician in charge of the study, not of the funder, and the results must always be made public if they have sufficient scientific validity.

Any request to hide results, to change or attenuate the content of a report, or to postpone the publication of results, will be categorically rejected.

#### **Obligation to peer review**

The general rule is to submit the results of a study to an independent peer review before making them public or submitting them to the media.

#### **Impartiality of publications**

Publications should describe all aspects of the study in an honest and balanced way without taking into account other interests, especially non-scientific ones. Scientific committee members should not exaggerate the results of the study in order to increase their chances of obtaining more funding for future research or to make their articles more attractive to the editor of a journal. A certain bias of selecting results that agree with the view of the physician in charge of the study and ignoring those that contradict it must be avoided. Authors of epidemiological articles must comply with the rules of quality journals in which possible conflicts

of interest are disclosed. The definition and order of authorship should be consistent with scientific publication practices. In this study, the list of investigating physicians will be systematically associated with all publications.

## **8. Statistical analysis**

The source data will be collectively analyzed for subgroup studies defined according to scientific criteria by a committee dedicated to this study.

Analyses will be performed using R software, with all required software packages, and JAGS, in their most up-to-date version at the time of analyses.

No hypotheses will be tested for either the primary or secondary objectives. A descriptive analysis of all evaluation criteria will be performed on the total population and on subgroups to be defined a priori according to the sample.

The variables collected at the end of the steady state, at maximal exercise, and during recovery (Rec + 2') will be expressed as mean, standard deviation (SD), median, quartiles.

Modeling of the kinetics of certain variables (VE-TV-BF-HR) will be performed and then a mathematical model will be developed to quantify and compare these kinetics between subgroups. Comparisons of kinetics between subgroups will be made using recently developed mixed-effects functional analysis of variance (FANOVA) methods.

The kinetics of some variables will be expressed as a function of developed power (in watts), metabolic power (VO2 in L/min), ventilatory flow (in L/min), HR expressed in absolute value, in % of the max HR reached and in % of the predicted value according to the formula maxHR = 210-0.65 x age).

## **9. Sample size**

1 000 patients with exercise intolerance after COVID are expected for the enrollment period.

## **10. Legal and ethical considerations**

### *10.1. Ethical considerations*

This study has been filed with the Commission Nationale Informatique et Liberté – CNIL and is registered in the public directory maintained by the French Health Data Hub.

### *10.2. Information to patients*

As is commonly done on admission to hospitals, a signed informed consent form will be attached to the administrative and medical file of the patient.

In the absence of an informed consent form, patients who have undergone CPET will be contacted and informed of the modalities of this study in order to sign an informed consent form ([Appendix 1](#)).

This will be done as long as it does not involve a disproportionate effort.

### *10.3. Pharmacovigilance*

In accordance with the Jardé law, pharmacovigilance reports of serious adverse events (SAEs) concerning drugs will not be collected during the study, nor transmitted to the pharmaceutical companies concerned.

Adverse events and SAEs will be managed by the investigators according to their usual practices.

### *10.4. Protocol amendment*

Any modification of the protocol will have to be discussed and approved by the steering committee and will be subject to an amendment.

Minor changes (editorial corrections to improve comprehension, spelling corrections, administrative changes ...) will result in an increase of the number after the dot in the version number: version 1.1 instead of version 1.0.

Major changes will result in an increase of the number before the dot in the version number: version 2.0 instead of version 1.0.

Major changes will be reported to the appropriate authorities.

### *10.5. Archiving*

The study data manager, who is also the study management center, will retain all study data for the following periods:

- Patient data: Retention in the controller's information system for up to 2 years after the last publication or, in the absence of publication, until the final research report is signed.
- Professional data: 15 years maximum from the end of the last research in which the health professional participated.

Following this, these data will be archived on paper or computer for a maximum of 20 years in accordance with the Cnil deliberation n° 2018-155 of May 3, 2018 (MR-004).

*10.6. Financial Partner*

This study will be conducted with the financial support of the Pharmaceutical Companies Menarini France and AstraZeneca.

## Appendix 2: CPET post-COVID questionnaire

Anonymized Center Code	Anonymized patient code	Sex	Age	Weight	Height
////	////	M/F	years	kg	cm

Date COVID	Date CPET (EFX)
month/year	day/month/year

Physical Activity Level before COVID-19							
Sport (h/week)		Work Activities		Daily Physical Activities			Seating Time
No	No						
YES	YES						< 4 h
< 4 h	With movement	Mainly Domestic (Inside)					4 – 7 h
4-6 h	Without movement	Leisure Time Activities (Outside ≥ 60 min /J)					> 7 h
6 à 10 h							
> 10 h							
Sport competition							

Main comorbidities							
Pulmonary Disease	Arterial hypertension	Cardiac Disease	Metabolic Disease	Chronic renal failure	Chronic Hepatic failure	Psychiatric condition	Cancer
No	No	No	No	No	No	No	No
YES	YES	YES	YES	YES	YES	YES	YES
Obstructive		Myocardiopathy	DT2			Anxiety Treated	Cured
Interstitial		Coronary disease	DID			Dépression Treated	Remission
Vascular		Valvular disease	Thyroid Insufficiency			Psychosis	Progression
Others		Congénital Disease	Others			Cognitive disorder	
		Chronic Heart Failure					
		Others					

COVID: initial clinical presentation							
Besoin en O2		CT-scan Parenchyma Extension			Symptomes non respiratoires		
No		No			No		
YES		YES			YES		
0.5-6 L/min		Mild < 10 %			Prolonged fever		
> 6 L/min		Moderate 10-24 %			Fatigue		
Hight Flow		Moderate-to-severe 25-49 %			Joints/muscle pain/stiffness		
Invasive ventilation		Severe ≥ 50 %			Headache		
					Anosmia and/or agueusia		
					Gastrointestinal		
					Neurological		
					Cardiac/Pericardial		

Symptoms Post COVID													
Dyspnoea	Fatigue	Cough	Muscle/ Joint pain	Anxiety	Agueusie	Anosmia	Headhache	Neurological	Gastro intestinal	Palpitations	Vertigo	Others	
No	No	No	No	No	No	No	No	No	No	No	No	No	No
Yes	Yes	Yes	Yes	Yes	Yes	Yes	Yes	Yes	Yes	Yes	Yes	Yes	Yes
Gasping for breath													
Shortness of breath													
Chest tightness													
Incomplete or unsatisfactory breathing													

Cardiac Evaluation																	
ECG				Echocardiography						MRI							
No		No						No									
Yes		Yes						Yes									
Normal		Normal						Normal									
Abnormal		Abnormal						Abnormal									

Questionnaires Scores													
Hosp. Anxiety and Depression Scale							Chalmers						
Anxiety		Depression						Fatigue					
Not Done		Not Done						Not Done					
Value		Value						Value					

Rest Pulmonary Function													
FEV 1		FVC		SVC		TICO							
(L.)		(L.)		(L.)		(mlco/min/mmHg)							
Value		Value		Value		Value							

Treatments with potential effects on exercise responses													
Pulmonary				Cardiovascular						Others			
No				No						No			
Yes				Yes						Yes			
Bronchodilatators				Betablockers						To be specify			
				Calcium inhibitors									

Maximal Borg Scale													
Dyspnoea				Fatigue				Muscular pain					
0 to 10				0 to 10				0 to 10					

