	
They include continuous recording of ergospirometer measurements and discontinuous recording of blood pressure, symptoms and blood gases.
 
In order to get rid of some of the variability of the results the export will only concern the measured data. Additional physiological data will then be obtained by applying the appropriate physiological calculation formulas in a strictly identical way whatever the brand of the ergospirometer. All these data (measured and calculated) will be transformed by the CPET-STUDIES application into a file called Finalized File.
 
Collection of clinical data
 
The clinical data of the patients will be collected on the medical file or a dedicated file (Excel or Word) by each practitioner. They will be filled in by the referring physician who alone knows the name and surname of his patients on the online platform. The identifying data of each patient will then be pseudonymized so that no one other than the referring physician can access them. All data is hosted by a health data host certified for the 6 HDS levels.
 
Clinical data are: sex, weight, age, height, date of COVID, physical activities before COVID, comorbidities, COVID-related symptomatology, usual treatments, Hospital Anxiety and Depression Scale (HADS) and Chalder fatigue scale questionnaires.
 
Access to the platform will be secured by identification with a login and a password
 
The patient's physiological and clinical data will be encrypted and pseudonymized when migrated and/or entered on the CPET-STUDIES.COM platform.
 
The content of the Finalized File will then be imported into a database, which contains only the clinical data associated with the patient's pseudonym.

Patient information	
As is commonly done on admission to hospitals, a signed informed consent form will be attached to the administrative and medical file of the patient.
 
In the absence of the signed informed consent form, patients who have undergone CPET will be contacted and informed of the modalities of this study, and asked to sign the informed consent form (see Appendix 1).
 
This will be done as long as it does not involve a disproportionate effort.

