## 2. Objectives of the study

### 2.1. Primary objective

**Kinetics of physiological responses and symptoms during CPET:** to describe by homogeneous subgroups of patients, the physiological responses and symptoms during CPET in COVID-19 subjects with persistent symptoms responsible for exercise intolerance.

Homogeneous patient subgroups will consider:

- the initial clinical presentation of COVID,
- any persistent symptoms other than exercise intolerance,
- clinical characteristics prior to COVID-19 infection (co-morbidities – regular habitual physical activity).

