### **6. Evaluation criteria**

#### **6.1. Primary endpoint**

To describe by homogeneous patient subgroups, physiological responses and symptoms during CPET in COVID subjects with persistent symptoms responsible for exercise intolerance.

Homogeneous patient subgroups will consider:

- the initial clinical presentation of COVID,
- any persistent symptoms other than exercise intolerance,
- clinical characteristics prior to COVID-19 (co-morbidities - physical activity level).

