## 7.2. Data collection

### 7.2.1. Clinical data

Clinical data recorded (see [Appendix 2](#)) include:

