#### **Appendix 4: Methodology of the CPET**

The main recommendations are:

- a. No need to record ventilatory measurements in the resting state
- b. Continuous recording of ventilatory and ECG measurements; and discontinuous (see below) recording of blood pressure, symptoms and blood gases during the following 3 phases:
  - A steady state phase of 3 minutes at constant load 20-30-40 or 50 watts, depending on clinical situation and body mass.
  - An incremental phase of 10-15 or 20 watts depending on the clinical situation and body mass.
  - A recovery phase for a minimum of 3 minutes without load, pedaling without load.
- c. Borg Dyspnea then Borg Muscle Fatigue
  - At the end of the steady state,
  - Every 2 minutes,
  - At maximal exercise,
  - At 3 minutes post exercise (Borg D + Borg F).
- c. Capillary or arterial blood gases including lactatemia if possible
  - At the end of steady state,
  - At maximal exercise,
  - Intermediate stages depending on clinical situation

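### The protocol contradicts itself on how serial Borg scores are captured: the form keeps only the maximum, the synopsis places symptoms in the ergospirometer data, and section 7.3 does not mention them

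*Protocol*

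**What the plan says.** **Objective.** The protocol's section 2.1 is headed "Kinetics of physiological responses and symptoms during CPET". The primary endpoint in section 6.1 is worded without kinetics: "To describe by homogeneous patient subgroups, physiological responses and symptoms during CPET in COVID subjects with persistent symptoms responsible for exercise intolerance". The synopsis objective also omits the word.

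**Measurement.** Section 7.2.1 names the Borg scale "for the collection of symptoms during CPET". Appendix 4 recommends dyspnoea and muscle-fatigue ratings "At the end of the steady state", every 2 minutes, at maximal exercise, and "At 3 minutes post exercise (Borg D + Borg F").

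**Capture on the form.** Section 7.2.1 opens with "Clinical data recorded (see" and refers to Appendix 2. The paragraph on symptoms during the test sits under that section. The only exercise-symptom block in Appendix 2 is "Maximal Borg Scale", with one 0 to 10 value each for dyspnoea, fatigue and muscular pain. It has no field for time, load or repeat readings.

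**Capture from the device.** The synopsis says that the source data held on each ergospirometer until migration include "discontinuous recording of blood pressure, symptoms and blood gases". Its own list of clinical data contains no Borg score.

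**Processing and analysis.** Section 7.3 describes averaging of measured variables and derivation of calculated variables for the Finalized File, and does not mention Borg scores. Section 8 summarises variables at the end of the steady state, at maximal exercise and at 2 minutes of recovery.

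**The concern.** Symptoms during exercise are part of the primary objective, and section 2.1 names their kinetics. A single maximum has no time course: it cannot show at what load or ventilation dyspnoea began to rise, or how far it had settled in recovery. The body of the protocol points sites to a form that asks for exactly that single value, while the synopsis points to another source.

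About 40 investigators are expected, taking part voluntarily and using different brands of ergospirometer. With the route unsettled, some may deliver a symptom series and others one number. Ratings that were neither entered nor exported cannot be recovered by any later analysis plan, so this has to be settled in the protocol and the form.

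**Working it through.** The protocol gives no figure to reproduce here, since it plans no hypothesis test and no sample-size calculation. The check follows the Borg score from the test to the analysis.

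| Step | Place in protocol | What happens to serial Borg scores |
|---|---|---|
| Measured | Appendices 3 and 4 | Rated repeatedly, where the recommendations were followed |
| Captured, route A | 7.2.1 and Appendix 2 | Only the maximum is kept |
| Captured, route B | Synopsis, data collection | Part of the ergospirometer source data to be migrated |
| Processed | 7.3 | Not mentioned |
| Summarised | 8 | Three time points apply to the variables collected |

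Routes A and B classify the same item differently: clinical data in section 7.2.1, physiological source data in the synopsis. Section 7.3 does not decide between them. The synopsis and section 7.2.2 limit the export to measured data, and neither says whether a rating given by the patient counts as measured.

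**What route A alone delivers**

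- Section 8 summary points: end of steady state (no), maximal exercise (yes), recovery (no). That is 1 of 3.
- Fixed Borg times in Appendix 4: end of steady state (no), maximal exercise (yes), 3 minutes after exercise (no). That is also 1 of 3, with none of the intermediate 2-minute readings.
- Per test, assuming an incremental phase of 8 to 12 minutes (not in the protocol) and taking the last 2-minute reading as the maximal one: 8/2 + 2 = 6 to 12/2 + 2 = 8 readings per symptom, of which the form keeps 1.

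**What complete serial capture delivers.** Even with every Appendix 4 rating in the file, only 2 of the 3 summary points in section 8 match exactly, because the recovery rating is recommended at 3 minutes and section 8 summarises recovery at 2 minutes.

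**Scale labels.** Appendices 3 and 4 rate breathlessness and muscle fatigue. The form asks for dyspnoea, fatigue and muscular pain. A value taken from the test record therefore does not map cleanly onto all three fields.

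**The case against.** The strongest objection is that a second route is stated. The synopsis counts symptoms among the source data that stay on the ergospirometer until migration, and says that the measured and calculated data become the Finalized File. The two items in section 7.3 are operations on the data, not an inventory of variables. Read as an inventory, they would also drop blood pressure and blood gases, which have no field in Appendix 2 either. Section 4.1 refers to a standardized export file whose variable list is not in the protocol, so its omissions cannot be asserted. This stands. A reader might infer that no route carries serial Borg scores to the analysis, and the documents do not support that.

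A reader might also infer that the symptom part of the primary objective cannot be described at all. That goes too far. Kinetics of symptoms rests on the heading of section 2.1 alone, and the endpoint in section 6.1 is partly served by peak symptoms by subgroup. Nor do the documents show that maximal scores lie near the top of the scale in most patients, so a ceiling effect forms no part of the point. That section 8 lists no symptom among the kinetics to be modelled is also not counted, since an analysis plan may cover it.

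The objection does not remove the conflict. The synopsis does not override section 7.2.1, which sends sites to a form with a maximum only. A hand-entered maximum would be redundant if the export reliably held the series. That suggests, without proving, that the form was meant as the symptom source.

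Finally, the data are retrospective and Appendix 4 gives recommendations only, so serial ratings may not exist everywhere. This stands as a limit on the fix.

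**Conclusion.** The concern holds as a contradiction over data capture for part of the primary objective. Section 7.2.1 with Appendix 2 keeps one maximal Borg value per scale, the synopsis implies migration of the serial record, and section 7.3 confirms neither.

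The loss is conditional. Where a site relies on the form, symptoms can be described by subgroup at peak only, with no time course and no value at two of the three summary points in section 8. Where the export does hold serial ratings, little or nothing is lost beyond the 2-minute versus 3-minute mismatch in recovery. The protocol does not allow a reader to say how many sites fall in each group. The count of 6 to 8 readings per symptom depends on the assumed test length; the count of 1 in 3 does not.

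**What to change.** Reconcile section 7.2.1, Appendix 2, section 7.3 and the synopsis so that one stated route carries serial Borg scores:

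1. Where the ergospirometer export already holds them, name serial Borg values with their time or load as Finalized File variables in section 7.3, and do not retype them.
2. Otherwise extend the Borg block of Appendix 2 to end of steady state, maximum and recovery, plus intermediate readings with load or time where they were recorded.
3. Record the minute of the recovery rating, because Appendix 4 and section 8 differ, and align the two sections.
4. Align the scale names on the form with Appendices 3 and 4.

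The change uses existing test records and needs no new examination. If every site had to type, the two extra fixed points for two symptoms in 1 000 patients come to 2 × 2 × 1 000 = 4 000 values, about 100 for each of 40 investigators. Adding all intermediate readings, under the assumed test length, raises this to (6 − 1) × 2 × 1 000 = 10 000 up to (8 − 1) × 2 × 1 000 = 14 000 values, or 250 to 350 each. This is why export should be used where it exists. Some values will be missing where a centre noted only the maximum, so the number of patients with a rating at each time point should be reported.
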